## I. Background and Significance of the Study

COPD is associated with sleep-disordered breathing (SDB) due to multiple factors, including airflow obstruction and lung hyperinflation in the emphysematous type [Know et al, 2009], hypercapnia caused by reduced ventilation during sleep [Lee et al, 2019] and nocturnal SaO2 levels below 90%[Czerwaty et al, 2022]. Many patients with COPD have been reported to exhibit a tendency toward impaired sleep quality [Azuma, 2014. Climaco, 2022].

In Japan as well, it has been demonstrated that reduced sleep quality among male urban workers with COPD is significantly associated with sleep-disordered breathing (SDB) [Azuma, 2014]. Poor sleep quality in patients with COPD is associated with worsening health status [Lin, 2023. Shorofsky, 2019], increases the risk of exacerbations, and hampers symptomatic improvement [Lin, 2023]. Although appropriate interventions to improve sleep quality are warranted, healthcare providers have relatively few opportunities to address sleep status or the daytime consequences of poor sleep in this patient population.

Bronchodilators, the mainstay of COPD treatment, are predominantly administered via inhalation, allowing direct delivery to the lungs and thereby ensuring therapeutic efficacy while minimizing systemic side effects. Bronchodilators, such as  $\beta$ 2-agonists and anticholinergic agents, have been reported to increase FEV1 and improve average nocturnal SaO2. However, incorrect inhalation technique may reduce their efficacy, leading to insufficient therapeutic effects [Sulaiman, 2016] . Furthermore, some studies have reported that improvements in sleep quality, respiratory symptoms, and quality of life (QOL) were not achieved [Krachman, 2021. Bouloukaki, 2015]. In recent years, with the diversification of inhalation devices and the increasing use of multiple inhaled medications, the prevalence of inhaler misuse has been reported to range between 37% to 75% [Lindh, 2022. Ahn, 2020. Ngo, 2019. Muller, 2017]. Furthermore, even after receiving education on inhalation techniques, 63.6% of patients continued to misuse inhalers [sauriasari, 2021], highlighting the importance of repeated instruction, particularly for elderly patients and those with COPD receiving multiple medications. Inhaler technique education is a crucial component of COPD management, and it should be delivered not only by pharmacists but also by nurses.

Previous studies [Sauriasari, 2021. Al-Kalaldeh, 2016] have primarily focused on the technical aspects of inhalation techniques. However, in nurse-led disease management education—which encompasses a wide range of topics such as disease education, nutritional management, and responses to exacerbations [Moriyama, 2010] —it cannot

be said that sufficient education is being provided regarding the appropriate use and administration of inhaled medications. Furthermore, patient education and guidance, which were traditionally delivered face-to-face, have increasingly incorporated information and communication technologies (ICT), such as telephone consultations, online videos, and mobile applications, particularly since the COVID-19 pandemic. Nevertheless, there are no existing reports evaluating the effectiveness of video conferencing for inhalation management education.

Based on the above, the central academic question of this study is whether inhalation management education provided by nurses via video conferencing can improve sleep quality in patients with COPD. By clarifying this relationship and examining the impact of inhalation management education, we aim to develop an effective educational program tailored to the specific characteristics of COPD patients. We believe that conducting this study will help maximize the therapeutic benefits of current treatments, thereby contributing to improved sleep quality, symptom alleviation, and enhanced quality of life (QOL), even among individuals with this chronic progressive disease.

Furthermore, since many COPD patients are elderly and may experience difficulty accessing medical facilities due to transportation challenges, this study may offer insights into enabling continuous care, regular technical assessments, and appropriate treatment even during outbreaks of emerging infectious diseases such as COVID-19.

## **II. Objective**

To investigate whether providing two sessions of patient education on inhalation technique and self-management via video conferencing, in addition to continuous inhalation therapy, improves sleep quality and quality of life in COPD patients compared to standard self-care support.

## **III. Methods**

### **1. Study Design**

A multicenter, block-randomized controlled trial involving patients with COPD.

### **2. Study Participants and Eligibility Criteria**

Patients in the stable phase of chronic obstructive pulmonary disease (COPD) who regularly attend Kumamoto University Hospital, Konan Hospital, or Iwakuni Municipal Nishiki Central Hospital, all of which provide internal medicine and respiratory care, will be eligible for participation in this study. Eligible participants must meet all of the inclusion criteria and none of the exclusion criteria listed below.

**(1) Inclusion Criteria**

1. Individuals aged 20 years or older at the time of obtaining informed consent.
2. Individuals who have been prescribed and continuously using inhaled medications for more than one month.
3. No restrictions regarding previous experience with inhalation instruction.
4. No hospitalizations due to COPD exacerbation within one month prior to study participation.
5. Individuals with coexisting obstructive sleep apnea syndrome (OSAS) and undergoing treatment with continuous positive airway pressure (CPAP) may be included, provided their symptoms are stable following CPAP initiation.
6. Individuals capable of operating a device such as an Android tablet, iPad, or personal computer. However, participants may still be eligible if a caregiver can operate the device on their behalf.
7. Individuals who have received approval from their attending physician.

**[Justification for Inclusion Criteria]**

1. The minimum age for participants to make an informed decision about joining this study was set at 20 years old.
2. Based on prior research, participants were defined as those receiving continuous inhaled medication therapy for at least one month, not new patients.
3. In cases of hospitalization due to COPD exacerbation, the first month post-discharge is difficult to assess whether symptoms like dyspnea or bronchodilator effects stem from the recovery process or inhaler management education. Therefore, the one-month mark, when symptoms are considered stable, was set as the starting point.
4. If symptoms are stable (fixed) after OVS diagnosis and CPAP initiation, the bronchodilator effect from proper inhaler use is considered independent of OVS presence and thus acceptable. If OSAS suspicion arises during pre-enrollment screening and is subsequently diagnosed, treatment takes priority. After consultation with the primary physician, the study will commence 3-6 months after CPAP initiation.
5. This requirement was established because the intervention in this study utilizes video conferencing. Participants unable to operate devices for video conferencing (e.g., Skype, Zoom) would necessitate unnecessary contact, potentially increasing participant burden and introducing bias.
6. This was established as a necessary requirement for conducting this study.

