#### 4. Allocation Method

Stratified block allocation will be used, with gender (male, female) and severity classification (Grade 1, 2, 3, 4) as allocation factors. Allocation of subjects to each treatment group will be performed by [name] at the Department of Basic Nursing Science, Kumamoto University Graduate School.

Following a pre-generated random allocation table, subjects will be sequentially assigned to treatment groups in the order of case registration. A registration confirmation document listing the subject registration number and group name will be issued. The allocation table will be retained by the person responsible for allocation and will not be disclosed to the Principal Investigator or Co-Investigators.

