**8. Evaluation Items****(1) Primary Evaluation Item**

Improvement in the Japanese version of the Pittsburgh Sleep Quality Index (PSQI-J)  
[Rationale]

The PSQI (Pittsburgh Sleep Quality Index) is a scale for evaluating sleep quality. It is the most widely used and standardized measure globally, employed in numerous clinical trials. A Japanese version, PSQI-J, has also been developed. Since this study aims to examine sleep quality improvement as an effect of inhalation management education, this scale was selected as the primary outcome measure.

The PSQI-J is a questionnaire assessing sleep status over the past month. It consists of 19 self-reported items and seven subscales: Sleep Quality, Sleep Onset, Sleep Duration, Sleep Efficiency, Sleep Difficulty, Sleep Medication Use, and Daytime Sleepiness. A total score ranging from 0 to 3 points (0–21 points total) is calculated, with higher scores indicating greater sleep impairment.

Assessment timepoints were at participant registration, the second intervention session, and study completion.

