## 10. Analysis Methods

### 1) Analysis of Primary Endpoint

#### Primary Endpoint: PSQI-J at 3 months post-educational intervention

Analysis of the primary endpoint will be performed using the Full Analysis Set (FAS). The change in PSQI-J for each group will be calculated, and between-group comparisons will be performed at a 5% significance level (two-tailed) using covariance analysis adjusted for the background factors of age and disease stage classification. A similar analysis will be performed secondarily using PPS as the analysis population.

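### The one-month wait after an exacerbation discharge is no longer than the PSQI-J recall period, so some baseline scores describe the recovery month; the effect is small and not a bias between arms

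*Protocol*

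**What the plan says.** Inclusion criterion 4 in the Protocol, section III.2, reads "No hospitalizations due to COPD exacerbation within one month prior to study participation". Its justification (item 3 of that list) gives the reason: "the first month post-discharge is difficult to assess whether symptoms like dyspnea or bronchodilator effects stem from the recovery process or inhaler management education". It concludes: "Therefore, the one-month mark, when symptoms are considered stable, was set as the starting point".

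Section III.8 (1) describes the primary measure: "The PSQI-J is a questionnaire assessing sleep status over the past month". On timing it says "Assessment timepoints were at participant registration, the second intervention session, and study completion". The enrolment list in section III.9 and Table 1 also place the first PSQI-J at registration.

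For the primary analysis, section III.10 states "The change in PSQI-J for each group will be calculated" and compares groups by "covariance analysis adjusted for the background factors of age and disease stage classification". Section III.4 stratifies allocation by "gender (male, female) and severity classification (Grade 1, 2, 3, 4) as allocation factors". Neither place names recent hospitalisation, and baseline PSQI-J is not among the named covariates.

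**The concern.** A one-month wait is enough for a measure of the patient's present state. The PSQI-J is a look-back over about a month. When the wait and the recall period have the same length, a patient registering on the first permitted day reports on precisely the month that the justification sets aside as hard to interpret. The wait protects the start date but not the baseline score.

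The later scores look back on later weeks. The second session comes four weeks after the first, which itself follows registration, and completion comes about eight weeks after the second. Their recall periods therefore lie essentially beyond the recovery month. In a recently discharged patient, natural recovery is then recorded as PSQI-J change, whichever arm the patient is in.

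At stake are the precision of the between-group comparison, its balance in a small trial, and the meaning of any within-group improvement that is reported.

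**Working it through.** **1. Inputs from the protocol.** Recall period: one month (III.8). Baseline: at registration (III.8, III.9). Recovery month: the first month after discharge (III.2, justification item 3). Earliest entry: one month (same item). Sample size: 17 per group required for a 5.0-point difference at two-sided 5% and 80% power, raised to 30 per group for dropout (III.5, rationale).

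**2. Overlap.** Take a month as 30 days and let d be the days from discharge to registration, d ≥ 30. The baseline recall covers days d − 30 to d, and the recovery month covers days 0 to 30. The share of the recall period inside the recovery month is

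overlap = max(0, 60 − d)/30.

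| d (days) | 30 | 37 | 45 | 52 | 60 or more |
|---|---|---|---|---|---|
| Overlap (days) | 30 | 23 | 15 | 8 | 0 |
| Overlap (%) | 100 | 77 | 50 | 27 | 0 |

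This step uses only the protocol's own time windows. Overlap disappears only when the wait equals the recovery month plus the recall month.

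**3. Scale for the size of effect.** The readable text gives no SD, so the 17 per group can be neither confirmed nor refuted. Solving the two-sample t test for 17 per group, a difference of 5.0 and 80% power gives an SD of about 5.05 (variance 25.50). It is used here only as a yardstick for the SD of change.

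**4. Assumed values.** The protocol does not say how many patients will register 30-60 days after discharge or how much PSQI-J recovers. Assume a share p of 5-20% and recovery r of 2-4 points at full overlap. Let overlap be uniform between 0 and 1 among those affected. The added change per patient then has

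- mean = p·r/2
- variance v = p·r²/3 − (p·r/2)²
- SD of the chance between-arm difference = √(2v/n)

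| p | r | Mean added to change | v | v/25.50 | Chance SD, n = 17 | Chance SD, n = 30 | Power, n = 17 |
|---|---|---|---|---|---|---|---|
| none | none | 0 | 0 | 0 | 0 | 0 | 79.9% |
| 0.05 | 2 | 0.05 | 0.064 | 0.25% | 0.09 | 0.07 | 79.8% |
| 0.05 | 4 | 0.10 | 0.257 | 1.0% | 0.17 | 0.13 | 79.5% |
| 0.20 | 2 | 0.20 | 0.227 | 0.9% | 0.16 | 0.12 | 79.6% |
| 0.20 | 4 | 0.40 | 0.907 | 3.6% | 0.33 | 0.25 | 78.5% |

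In the last row the standard error of the difference at 17 per arm goes from 1.73 to 1.76. If all 30 per group are analysed, the same row lowers power only from 96.5% to about 96.0%.

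**5. A harsher bound.** Suppose every affected patient registers at day 30, so overlap is full. The added variance is then p(1 − p)r², at most 0.20 × 0.80 × 16 = 2.56. With SD 5.2 (the upper end of the 5.05-5.20 that 17 per group implies under the normal approximation), power at 17 per arm falls from 80% to 76%. An excess of three such patients in one arm of 30 would shift the between-arm difference by 3 × 2/30 = 0.2 to 3 × 4/30 = 0.4 points.

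**The case against.** The strongest reply is that the primary test compares change between randomised arms, and the control arm carries the same recovery in expectation. A reader might infer that the mismatch inflates the apparent effect of education. The documents do not support that: no bias between arms follows, and the overstated within-group change is not what section III.10 tests. This part of the reply stands.

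The affected group may also be very small. If registration is unrelated to the time of discharge, having 20% of patients in one particular 30-day window implies about 0.20 × 365/30 = 2.4 exacerbation discharges per patient-year, and 5% implies about 0.6. The trial recruits stable-phase outpatients with their physician's approval. This makes the upper assumption look strained, and the true number could be zero. However, these entry conditions concern the patient's state at registration and do not alter what the questionnaire recalls.

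On wording, one might be tempted to say that the protocol declares the month unassessable, or that criterion 4 contradicts itself. It says only that attribution is difficult in that month, it speaks of dyspnoea and bronchodilator effects rather than sleep, and it counts from discharge rather than admission. The criterion does deliver a stable start date. It is incomplete for a recall instrument, not self-contradictory.

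Finally, a sensitivity analysis could sit in an analysis plan that is not shown. That is fair, but entry timing and baseline timing are fixed in the protocol, and no later analysis can change which month a completed questionnaire described.

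**Conclusion.** The mismatch is real and follows from the protocol's own statements: the wait equals the recall period, so it cannot clear it. It affects only patients registering between one and two months after discharge, and nothing else in the protocol removes it. By contrast, the 3-6 months set after CPAP initiation in patients newly diagnosed with sleep apnoea does clear a one-month recall.

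The consequence is minor. The expected between-group difference is unchanged. Under the assumed 5-20% affected and 2-4 points of recovery, mean change in each arm is overstated by 0.05-0.40 points, its variance rises by about 0.3-3.6%, and power at 17 per arm falls by at most about 1.4 percentage points (79.9% to 78.5%), or to about 76% if all affected patients have full overlap. The overlap figures are firm apart from the 30-day convention. The size figures rest on assumed p and r and a back-calculated SD. This is a worthwhile refinement, not a threat to the trial's conclusion.

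**What to change.** Preferred: reconcile criterion 4 and its justification with the PSQI-J recall period. State that the interval runs from discharge, and require the recovery month plus the recall month: no hospital stay for COPD exacerbation ending within about two months before the registration PSQI-J. Patients discharged more recently register, and complete the baseline, once that time has passed. Delaying registration, rather than the questionnaire alone, keeps the baseline ahead of random assignment, as the Research Outline intends.

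Cost: a one-line amendment and no extra visit. Recently discharged patients wait up to one more month, and a few may be lost near the registration limit of 30 June 2026. The enrolment form already asks about hospitalisation in the past six months, but the item as listed names neither date nor cause, so the date and cause of discharge must be recorded.

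If recruitment makes the longer wait undesirable, keep the timing, add baseline PSQI-J as a covariate in the primary model, and add a sensitivity analysis excluding patients registered within two months of discharge. This is lighter but weaker: the affected baselines stay in the primary analysis, and the covariate can absorb only part of the artefact.

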## **(2) Exclusion Criteria**

Participants will be excluded if they meet any of the following criteria:

1. Presence of other respiratory diseases such as asthma or interstitial pneumonia.
2. Diagnosis of advanced cancer, including lung cancer.
3. Restricted thoracic mobility due to thoracic deformities or trauma.
4. Presence of diseases that cause dyspnea, such as cardiac disorders.
5. Sleep-disordered breathing in which central apnea–hypopnea index (AHI) accounts for the majority of events.
6. Diagnosis of dementia or psychiatric disorders.

### **[Justification for Exclusion Criteria]**

1. This criterion is intended to ensure accurate assessment of the effects of the educational intervention specific to COPD patients. Asthma will be definitively excluded through a fractional exhaled nitric oxide (FeNO) test at the time of study enrollment.
2. Advanced cancer may affect sleep quality due to psychological stress or disease burden, which could confound the study results.
3. In cases where thoracic movement is restricted, dyspnea may not respond to bronchodilation from inhaled medications, limiting the ability to assess intervention effectiveness.
- 4–5. Symptoms such as breathlessness caused by cardiac disease or central sleep apnea are unlikely to improve through the pharmacological effects of inhaled bronchodilators, making it difficult to evaluate the intervention's effectiveness.
6. Exclusion of participants with psychiatric or cognitive disorders is necessary to avoid potential confounding effects on sleep quality and to ensure participants can make autonomous decisions regarding study participation.

## **3. Subject Registration**

After approval by the Kumamoto University Ethics Committee, the principal investigator or co-investigator/collaborator will receive referrals of patients meeting the eligibility criteria from the attending physicians at the collaborating research institutions. The principal investigator or co-investigator/collaborator will then provide an explanation of the study at the date, time, and location specified by the patient. The purpose, significance, methods, and ethical considerations of the study will be explained verbally and in writing, and written informed consent will be obtained. After obtaining consent, contact the Principal Investigator to obtain a subject identification code and register the subject in the study.

#### 4. Allocation Method

Stratified block allocation will be used, with gender (male, female) and severity classification (Grade 1, 2, 3, 4) as allocation factors. Allocation of subjects to each treatment group will be performed by [name] at the Department of Basic Nursing Science, Kumamoto University Graduate School.

Following a pre-generated random allocation table, subjects will be sequentially assigned to treatment groups in the order of case registration. A registration confirmation document listing the subject registration number and group name will be issued. The allocation table will be retained by the person responsible for allocation and will not be disclosed to the Principal Investigator or Co-Investigators.

#### 5. Target Sample Size and Rationale

##### Target Sample Size:

- Intervention group: 30 participants
- Control group: 40 participants
- **Total:** 60 participants

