##### Rationale for Sample Size:

There are no previous studies that have specifically examined the impact of inhalation management education on sleep quality. In prior studies, the mean PSQI (Pittsburgh Sleep Quality Index) scores among patients with COPD ranged from 8.3 to 11.5, with a commonly used cutoff score of 5.5 to indicate poor sleep quality. Based on this, we assumed a mean reduction of 5.0 points in the PSQI-J score at 3 months in the intervention group.

Using a two-tailed test with a significance level of 5% ( $\alpha = 0.05$ ) and a power of 80% ( $\beta = 0.20$ ), the required sample size was calculated to be 17 participants per group.

[figure not shown]
However, considering that many participants are older adults who may face challenges in consistently using personal computers or video conferencing tools, a higher dropout rate than usual is expected. Therefore, we increased the target enrollment to 30 participants per group, for a total of 60 participants.

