## **11. Study Period**

Registration Period: Study Approval Date ~ June 30, 2026

(Last Observation Date for Last Patient: ~ December 31, 2026)

Implementation Period (Total Study Period): Study Approval Date ~ March 31, 2030

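### The control-arm target of 40 contradicts the stated total of 60 and the 30 per group in the sample size rationale

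*Protocol*

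**What the plan says.** The list under Target Sample Size in protocol section III.5 has three lines: "Intervention group: 30 participants", "Control group: 40 participants" and "Total: 60 participants".

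The Rationale for Sample Size that follows works with equal groups throughout. It reports that "the required sample size was calculated to be 17 participants per group", and then, to allow for dropout, "we increased the target enrollment to 30 participants per group, for a total of 60 participants".

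Two sections describe the randomisation. Section III.1 calls the trial "A multicenter, block-randomized controlled trial involving patients with COPD". Section III.4 specifies blocks stratified by gender and severity grade, and adds: "Following a pre-generated random allocation table, subjects will be sequentially assigned to treatment groups in the order of case registration". Neither gives an allocation ratio. Section III.11 ends registration on a date ("Registration Period: Study Approval Date ~ June 30, 2026") and gives no number of participants.

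**The concern.** The arm targets and the total in one three-line list cannot all be right. Read alone, the list leaves open whether 60 or 70 participants are planned, and whether the arms are meant to be equal or 3:4.

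The planned sample size is a headline design figure that sites and the ethics committee rely on. A site that followed the control line literally would recruit towards a target that the rationale does not support. Because no ratio is stated in sections III.1 or III.4, the targets in III.5 are the only figures from which a reader can infer one, and they conflict. The calendar end to registration does not settle the number either.

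**Working it through.** **Inputs, all from protocol section III.5**

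- Target list: intervention 30, control 40, total 60.
- Rationale: 17 per group required, raised to 30 per group, total 60.
- Design values: two-sided 5% significance level, 80% power, 5.0-point mean reduction in PSQI-J.
- The text gives no standard deviation (SD) and no dropout rate. A figure at this point is not reproduced in the copy reviewed.

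**Step 1: the totals**

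| Source | Arms | Sum | Stated total |
|---|---|---|---|
| Target list | 30 + 40 | 70 | 60 |
| Rationale | 30 + 30 | 60 | 60 |

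The rationale reproduces its own total exactly. The list exceeds its total by 70 − 60 = 10. The control target is 40/30 = 1.33 times the rationale's figure, or 33% higher.

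**Step 2: can dropout or unequal allocation reconcile the list?**

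- Dropout: going from 17 to 30 implies a loss of 1 − 17/30 = 43.3%. Going from 17 to 40 would imply 1 − 17/40 = 57.5%, and nothing in the text proposes a separate allowance for the control arm.
- Unequal allocation: a 3:4 ratio gives 30 + 40, which is still 70.

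The conflict lies in the sum itself, so neither route removes it.

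**Step 3: effect on power**

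This step is illustrative, because the SD must be assumed. The SD is back-solved from the plan's own 17 per group, using a two-sample t-test (noncentral t). Power of 80% at two-sided 5% needs a standardised difference of d = 0.9910 with 17 per group and d = 1.0237 with 16 per group. A calculated requirement of 17 therefore implies d between these values, and SD = 5.0/d gives:

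- 5.0/0.9910 = 5.05
- 5.0/1.0237 = 4.88

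Under a normal approximation the implied SD is 5.05 to 5.20 instead.

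The completer counts assume that the loss which takes 30 to 17 applies equally in both arms, so a control arm of 40 becomes 40 × 17/30 = 22.7, about 23.

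| Intervention : control | Power at d = 0.9910 | Power at d = 1.0237 |
|---|---|---|
| 30:30, no dropout | 96.5% | 97.4% |
| 30:40, no dropout | 98.1% | 98.7% |
| 17:17, after 43.3% loss | 80.0% | 82.5% |
| 17:23, after 43.3% loss | 85.5% | 87.7% |

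Neither reading takes power below the planned 80%.

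**The case against.** The strongest reply is that this is one wrong number which the document itself corrects. The total appears twice as 60 and never as 70. The rationale follows the list directly and derives 30 per group. Power is adequate on either reading, and the planned covariance analysis is valid under either ratio. The missing ratio is an omission rather than an error, equal groups in the rationale already imply 1:1, and nothing suggests that the allocation table is otherwise. The power figures rest on an SD and a dropout rate that the text does not state.

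Much of this stands. The ambiguity belongs to the target list, and the rationale points clearly to 30. The power figures are illustrative and the finding does not depend on them. Stating the ratio and checking the table are precautions, not separate faults.

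The objection does not remove the contradiction. The control target is an operational figure, it is wrong as written, and no section supports a larger control arm or gives a reason for one.

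**Conclusion.** The concern holds. The control target of 40 is inconsistent with the total of 60 immediately below it and with the 30 per group in the rationale. It overstates planned enrolment by 10, all in the control arm.

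The intervention target, the total in both places and the per-group figure all agree on 30 + 30, so 40 is most likely an error for 30. The sections on randomisation do not confirm this directly, because they state no ratio.

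This conclusion rests only on addition and on the protocol's own figures. The statement that power is little changed rests on the back-solved SD and, for the completer figures, on equal loss in both arms. The point should be fixed, but it does not threaten the validity or the power of the trial.

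**What to change.** In the target list of section III.5, change the control target from 40 to 30, so that it agrees with the total and with the rationale.

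Two optional precautions would close the matter:

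- State 1:1 allocation in section III.4.
- Ask the person responsible for allocation to confirm that the pre-generated table is 1:1, without showing it to the investigators, since section III.4 keeps it from them.

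If the table is 1:1, the cost is one number, one sentence and one check, with no change to enrolment. If it is not, the arm targets and total in section III.5 and the ratio in section III.4 must be restated to match it. Planned enrolment could then change, by up to 10 if the arms really are 30 and 40.
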